The CBD will be shipped to and stored in the Children's of Alabama (COA) Pharmacy Department and dispensed by the Investigational Pharmacy Staff at COA. All storage and accountability of the CBD will be handled by the COA Investigational Pharmacy Staff. The CBD will be dispensed by the COA Investigational Pharmacy Staff listed on the protocol. The CBD Medication orders will only be filled at the COA Investigational Pharmacy only. The principal investigator will submit a medication order the COA Investigational pharmacy, the pharmacy will fill the medication order and dispense the CBD to the study coordinator. The study coordinator will deliver the patient's CBD medication order, dosing instructions and package leaflet information (provided by GW Pharma) to the study patient.

The Investigator's Brochure provides additional information for the CBD formulations (100mg/mL) used in our protocol. Information Leaflets created by GW for 100mg/mL solution for study participants using the CBD product are included in the attached documents. Also, Physician Prescribing Information documents for 100mg/mL oral solution are attached for review. We are only using the 100mg/mL solution for this expanded access protocol. The manufacturer, GW Pharma, will supply the 100mg/mL solution for this IND. The higher concentration will provide the least amount of alcohol that can be accurately dispensed by the caregiver. We have confirmed that both of the CBD oral solutions (25 mg/mL and 100 mg/mL) contain 79 mg/mL of ethanol.

Risks, Side Effects, Discomforts, and Inconveniences:

The following are risks and discomforts that you may experience during participation in this research study. Some side effects occurred in more than 10% of study participants who have previously taken CBD for seizures/epilepsy. These side effects may or may not be related to CBD and include:

- diarrhea,
- fatigue (feeling tired)
- changes in liver function tests, change in blood counts which can affect the clotting of the blood (platelet), changes in seizure medications levels measured in the blood,
- decreased or increased appetite
- weight loss or weight gain
- difficulty walking
- rash,
- feeling drunk, sleepy or abnormal
- convulsions

As with any drug, not all risks are known. If participants experience any side effects, they will be instructed to inform the study doctor or research staff. All side effects will be treated appropriately.

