^g An EEG will be performed at the first annual (12 month) study visit. If participant has already pasted this visit, the EEG will be performed at their next study visit.

CRFs for this program were created using the NINDS common data elements CRFs and other common Epilepsy data collection resources.

Withdrawal of Participant Consent and Early Termination/Discontinuation of Study Drug:

Study participation may be discontinued for any of the following reasons:

- Administrative decision by the investigator or GW Research Ltd or Regulatory Authority.
- Subject decision to withdraw consent/assent for study.
- Withdrawal of parent/legal authorized representative consent.
- Pregnancy.
- Evidence of allergy to administered products.
- Lost to follow up
- Patient non-compliance
- Protocol deviation that is considered to potentially compromise the safety of the patient.
- In Investigator's judgement, development of active medical condition/treatment that impacts study activities.
- Intolerable adverse event as judged by study investigator and participant.
- Serious Adverse Event, which in the investigator's opinion compromises the safety of the patient.
- ALT or AST >8xULN
- ALT or AST >5xULN for more than 2 weeks
- ALT or AST >3xULN and (TBL >2xULN or INR >1.5)
- ALT or AST >3xULN with the appearance of fatigue, nausea, vomiting, right upper quadrant pain or tenderness, fever, rash, and/or eosinophilia (>5%)
- For any clinically significant (> 3 x ULN) elevation of ALT or AST in children under 21 years of age being treated with Epidiolex in an Expanded Access IND, the following laboratory measures, at minimum, should be assessed within 72 hours: repeat ALT/AST, total bilirubin, alkaline phosphatase, and GGT.
- All trial subjects with elevated LFTs should be followed until all abnormalities return to the baseline state as assessed by the investigator with AST/ALT < 3X ULN.
- If a subject has elevated LFTs (>3x ULN) and is on valproic acid the subject must stop the CBD and the LFTs must be monitored until the return to baseline state. If the subject has shown an improvement in their seizure frequency with the addition of CBD the option to "rechallenge" CBD will be at the discretion of the study PI. It would require that the subject taper off valproic acid and be on a stable dose of antiepileptic medication for 30 days prior to restarting the CBD. They would have repeat baseline labs (CBC, CMP and AED levels) prior to restarting the CBD.

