Adverse Events (AEs) for this study are defined as the appearance of (or worsening of any pre-existing) undesirable sign(s), symptom(s), or medical condition (s) that may occur after the patient's signed the informed consent for the study. Abnormal laboratory values or test results occurring after the informed consent is signed constitutes adverse events only if they induce clinical signs or symptoms, are clinically significant, require therapy, or changes in study medication(s).

AEs that begin or worsen after the informed consent should be recorded in the Adverse Event CRF and will be entered in the UAB CBD data coordinating center database. Conditions that are already present at the time of informed consent will be documented as part of the patient's medical history. Subjects and their families will be provided with contact information in order to notify study personnel of any adverse events, with availability at all times. Upon notification of an AE, a determination will be made by study personnel with regard to whether the AE is study related. This determination will be made within 24 hours of receipt of documentation of the AE. If the AE has involved participation of any other medical personnel or facilities, documentation of that activity will be obtained by study personnel for review. The AE will be monitored until it has resolved by the study investigator. AEs will be assessed to determine the following parameters: severity, duration, relationship to the CBD administration, action taken or treatment instituted, and whether the AE meets the criteria for a serious AE. Adverse Events will be assessed according to the Common Terminology Criteria for Adverse Events (CTCAE).

All clinically significant abnormalities noted upon physical examination, or other diagnostic test results should be reported as an AE, except for baseline measurements that may be considered part of the medical history. In addition, all clinically significant AEs that continue at Study Termination should be followed up by the investigator and evaluated with additional tests if necessary, until the underlying cause is diagnosed or resolved, or is determined to have resolved with sequelae. All AEs will be evaluated for

intensity and causal relationship with use of the study medication (or study procedures if applicable) by the investigator.

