## Statistical Analysis Plan

The UAB Pediatric CBD Program enrolled 89 treatment resistant epileptic children ages 1-19 years old. All study participants received Epidiolex drug (Cannabidiol; CBD) as an add-on to their previously stable anticonvulsive treatment after baseline assessment. Participants received a starting dose of CBD at 5 mg/kg/day in twice daily dosing and titrated by 5 mg/kg/2 weeks up to 25 mg/kg/day, with a maximum dose of 50 mg/kg/day. Seizure frequency, severity, and adverse events together, with other clinical participant measures, were assessed at baseline and bi-weekly for the duration of the study.

The first 12-months (1-year) of follow-up data were analyzed as follows:

1. The primary outcome measures included:

- a. Severe adverse events (increase in seizure frequency by more than 100% leading to emergency room visit or hospitalization),
- b. Change in resting blood pressure or heart rate by 25% if considered significant by managing neurologist,
- c. Any change in, CBC, CMP, Liver function tests (LFTs), Urinary Analysis or Antiepileptic drug (AED) levels considered by managing neurologists as clinically significant. Clinically significant will be determined by using the Common Toxicity Criteria for Adverse Events (CTCAE) Version 4.03. Adverse events (AE) categorized as a grade 3 or above will be considered clinically significant. Adverse Events graded 4 or above will be considered severe adverse events (SAE).

The analysis plan was focused on safety. The information on safety was tabulated as the percent of participants with each safety outcome AE and SAE, or others reported as meaningful as well as the number of occurrences of each AE and SAE. This enabled an event rate calculation per exposure time as well as the average number of occurrences per participant with an AE or SAE.

2. The secondary analysis assessed the frequency and severity of seizure outcome measures to include:

- a. Mean (SD) and median (IQR) decrease in seizure frequency as measured in total number of seizures per month.
- b. Mean (SD) and median (IQR) decrease in seizure severity as measured by the Chalfont Seizure Severity Scale (Duncan & Sander, 1991, JNNP).

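### The only planned analysis of serial laboratory values is a judged count of CTCAE grade 3 or above; no table shows change over time, shift from baseline, or multiples of the upper limit of normal

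*SAP*

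**What the plan says.** In the SAP, primary outcome 1c takes in changes in CBC, CMP, liver tests, urinalysis and antiepileptic drug levels that are "considered by managing neurologists as clinically significant". It then defines the term by CTCAE version 4.03: "Adverse events (AE) categorized as a grade 3 or above will be considered clinically significant". The protocol's Data Analysis section has the same rule. Safety data are to be "tabulated as the percent of participants with each safety outcome AE and SAE, or others reported as meaningful", together with numbers of occurrences.

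The protocol schedules laboratory panels at baseline and repeatedly in year 1. Its sections on withdrawal and on dosing adjustment set out liver criteria for stopping CBD:

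- ALT or AST above 8 x ULN;
- above 5 x ULN for longer than two weeks;
- above 3 x ULN with raised bilirubin or INR;
- above 3 x ULN with symptoms or eosinophilia;
- a separate rule, also at 3 x ULN, for children taking valproic acid.

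Both sections describe an elevation above 3 x ULN as clinically significant and call for repeat tests within 72 hours. The risks section lists liver-test and platelet changes as possible side effects, with the caveat "These side effects may or may not be related to CBD and include".

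**The concern.** The SAP says its focus is safety, yet the repeated laboratory values inside its primary outcome are reduced to one yes/no classification. The secondary seizure outcomes get means, medians, rank tests and a longitudinal spline model. Laboratory values are also missing from the protocol's list of exploratory data to be summarised descriptively and modelled over time.

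Two things are lost. The first is any shift in liver tests or platelets that affects many children but takes few or none of them to grade 3. The second is the protocol's own liver scale: a grade on one analyte carries no duration and no joint condition with bilirubin, INR or symptoms. A reader of the planned output could not say how many children passed 3 x ULN, how high values went, or which stopping criterion was met. The protocol gives renal and liver monitoring as a purpose of its safety laboratory tests, so these are figures a reader will want.

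**Working it through.** **The plan's own precision figures.** The protocol gives half-widths of two-sided 90% intervals at n = 100. For a proportion of 0.10: 1.645 x sqrt(0.10 x 0.90 / 100) = 0.049, as stated. For a mean: 1.645 / sqrt(100) = 0.164 SD, as stated. At the 89 children in the SAP these become 0.052 and 1.645 / sqrt(89) = 0.174 SD. For a 95% interval the latter is 1.96 / sqrt(89) = 0.208 SD. A mean laboratory change could therefore be estimated with useful precision.

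**How much data is reduced.** The laboratory footnote to the protocol's schedule of events gives 4-weekly panels to month 6 (weeks 4, 8, 12, 16, 20, 24), then months 9 and 12: 8 after baseline. The visit text omits CBC and CMP at Study Visit 11 (month 9), leaving 7. With all 89 children followed, 7 x 89 = 623 and 8 x 89 = 712 panels.

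**What the planned output can show.**

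| Quantity | Shown by planned output? |
|---|---|
| Judged grade 3+ laboratory events | Yes (1c) |
| Child stopped under a liver rule | Yes, as an adverse event, without criterion or multiple |
| Children above 3, 5 or 8 x ULN | No |
| Duration above 5 x ULN, or joint ALT/AST with bilirubin or INR | No |
| Change from baseline by visit, baseline-to-worst shift | No |

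**Illustration 1 (assumed rates).** Suppose 10% of children have some liver-test change: 0.10 x 89 = 8.9 children. If a fraction f of these reach grade 3, the expected count is 8.9f, and the chance of no event is (1 - 0.10f)^89.

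| f | Expected grade 3+ | P(no event) |
|---|---|---|
| 5% | 0.45 | 0.64 |
| 10% | 0.89 | 0.41 |
| 25% | 2.2 | 0.105 |
| 50% | 4.5 | 0.01 |

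**Illustration 2 (single draw, assumed normal values, SD of change equal to between-child SD).** With a cut-off 3 SD from the mean, a shift of 0.3 SD in every child moves the expected count beyond it from 89 x (1 - Phi(3)) = 0.12 to 89 x (1 - Phi(2.7)) = 0.31. Counting the worst of eight draws under the same assumptions (which imply a within-child correlation of 0.5), it moves from 0.81 to 1.95. Either way the count barely registers a shift that exceeds the 0.208 SD half-width of a 95% interval for the mean change.

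**The case against.** The strongest reply is that the safety table is wider than outcome 1c. It admits other events reported as meaningful, and the protocol's Adverse Events section makes a laboratory abnormality an adverse event if it causes symptoms, needs therapy or leads to a change in study medication. Any child stopped under a liver rule meets that last condition at any grade. This stands: a reader might infer that the primary safety table would show nothing, and the documents do not support that.

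Three other strong readings also fail:

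- **That new and pre-existing elevations cannot be told apart**, because entry excludes only ALT or AST above 5 x ULN. Outcome 1c concerns change, and the protocol counts as adverse events only findings that appear or worsen after consent, with existing conditions going to medical history.
- **That the protocol names liver and platelet changes as CBD effects seen in over 10%.** Its words are "Some side effects occurred in more than 10% of study participants who have previously taken CBD for seizures/epilepsy", and causality is left open. The same list includes difficulty walking and convulsions; Table 2 puts gait disturbance and convulsion at 5% each of 213 patients, and has no liver or platelet entry.
- **That the 3 x ULN criteria necessarily fall below grade 3.** The documents give no CTCAE cut-offs. If grade 3 began at 3 x ULN, every liver criterion would register in 1c, though unlabelled.

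It is also fair that continuing detection of harm rests with the DSMB and with per-child liver monitoring, not with this 12-month analysis. And a count per criterion is not simply read from the routine panels: INR is in no scheduled panel, symptoms must be linked to values, and scheduled draws 4 weeks to 3 months apart rarely settle a two-week duration.

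None of this supplies a summary of values over time or in multiples of ULN.

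**Conclusion.** The concern holds as a gap in reporting scale. Followed exactly, the grade 3 rule gives a less informative answer to the primary safety question than data already collected allow. It hides no child who was stopped for liver reasons, but it leaves the multiple reached, the criterion met and any sub-threshold cohort shift out of every planned table.

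The size cannot be fixed from the documents, which give no laboratory SDs, expected rates or CTCAE cut-offs. Under the assumed range in illustration 1, 8.9 affected children shrink to between 0.45 and 4.5 counted events. Illustration 2 shows direction only, because its normality, uniform shift and cut-off are assumptions. The points about duration, joint conditions and trend depend on none of these.

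Separately, the documents use two meanings of clinically significant for ALT and AST: grade 3 or above in the analysis, above 3 x ULN in the liver monitoring text. Whether they coincide cannot be determined from the documents, and the passages must be reconciled. This is worth correcting, at moderate priority.

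**What to change.** Keep the grade 3 count and add to SAP outcome 1c, as descriptive output:

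1. Change from baseline by visit with 95% intervals, for ALT, AST and bilirubin on the log scale and for platelets, hemoglobin and WBC. State which panel is baseline, since the protocol allows the pre-enrolment panel to stand in for the one at Study Visit 1.
2. A baseline-to-worst shift table for ALT and AST in the protocol's own bands: up to 3, above 3 to 5, above 5 to 8, and above 8 x ULN.
3. The number of children recorded as meeting each liver stopping criterion, including the valproic acid rule, with the number who lacked the INR, symptom or duration data needed to judge it.

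Reconcile the two uses of clinically significant for ALT and AST, and the footnote and visit text on the month 9 panel.

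The cost is SAP wording and a little more laboratory output. Items 1 and 2 use values already collected, assuming the CMP includes ALT, AST and bilirubin, which the documents do not spell out. Item 3 also needs adverse event and discontinuation records. No new test is needed, and no dose or stopping rule changes.

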The analysis plan for frequency and severity of seizures (secondary outcome measures) assessed the pattern of change over time relative to baseline. The non-parametric Friedman's test was used since seizure frequency and severity outcome measures were not normally distributed. Wilcoxon's signed rank test with Bonferroni's multiple comparison correction was utilized as a post-hoc analysis for pairwise comparisons between baseline and each post-baseline time point.

Further parametric analysis used the generalized least squares statistical techniques for modeling longitudinal data, an extension of mixed effects models that accommodates heteroscedacity and correlation within group errors (Pinheiro and Bates, 2000), after normality of outcome measures were achieved through log-transformation methods. The longitudinal analysis included each month following baseline up to the 12-month endpoint, with a log transformation of seizure measures regressed on time (months), gender, and several identified baseline clinical variables including number of AEDs, number of AEDs tried, and history of epileptic surgery. A cubic spline with 4 knots (carefully chosen with AIC and BIC) was put on time to capture the non-linear trend in seizure outcome measures. AIC and BIC also aided in the choice of the specified correlation structure for this analysis.

Effectiveness of CBD exposure on the population of interest was established with contrast estimates of percentage reduction in seizure outcome measures at each post-baseline time point relative to baseline from model.

Both parametric and non-parametric methods were repeated using last observation carried forward (LOCF) principle on the data instead of complete cases of the data. An alpha level of 5% was used to achieve statistical significance.

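### Holm's step-down could replace single-step Bonferroni in the post-hoc signed-rank tests: same family-wise 5%, never fewer rejections, and a gain that depends on an effect pattern the documents do not give

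*SAP*

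**What the plan says.** The SAP's secondary analysis of seizure frequency and severity "assessed the pattern of change over time relative to baseline". Friedman's test comes first. Then come Wilcoxon signed-rank tests, to which a Bonferroni "multiple comparison correction was utilized as a post-hoc analysis for pairwise comparisons between baseline and each post-baseline time point". On the error rate the SAP says only "An alpha level of 5% was used to achieve statistical significance"; it does not state sidedness.

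The number of signed-rank comparisons is not given. Two other sentences bear on it:
- For the generalized least squares (GLS) model, "The longitudinal analysis included each month following baseline up to the 12-month endpoint". That points to 12, but it describes the model and not the signed-rank tests.
- Outcomes "were assessed at baseline and bi-weekly for the duration of the study". That would give up to about 26 time points in a year.

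The SAP also does not say whether frequency and severity share one family, or how the repeats using last observation carried forward (LOCF) are counted. It plans no simultaneous confidence intervals for the signed-rank tests. It bases effectiveness on contrasts from the GLS model. The text is in the past tense throughout.

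**The concern.** Single-step Bonferroni holds every test to 0.05 divided by the number of tests, however many of the others are clearly significant. Holm's step-down starts at that threshold and relaxes it after each rejection. It needs no assumption that Bonferroni does not need. Where no Bonferroni-adjusted intervals are planned, the usual practical reason to prefer the simpler method is absent.

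What is at stake is how the time course reads in the non-parametric analysis. If a moderate reduction is present at many time points, Bonferroni would flag fewer of them than a method with the same error guarantee. The analysed sample may also be smaller than the 89 enrolled. The main analysis uses complete cases, and the protocol (Recruitment and Enrollment) sets no minimum duration and lets participants stop at any time.

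**Working it through.** **Inputs from the documents.** Alpha 0.05 (SAP); signed-rank tests with Bonferroni (SAP); n = 89, since the program "enrolled 89 treatment resistant epileptic children".

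**Inputs assumed.** Two-sided tests. Number of comparisons m = 12, with 26 as the high case (52 weeks / 2). Complete cases n = 60 as a low case. Standardized change d = 0.2 to 0.8 SD of the change score. Correlation between time points 0.5; 0.8 was also run.

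**Step 1. Reproduce the plan's 5%.** The Bonferroni threshold is 0.05/12 = 0.0042, and 12 × 0.05/12 = 0.05. If the tests were independent, the family error would be 1 − (1 − 0.05/12)^12 = 0.0489; for m = 26 it is 0.0488. The stated 5% is met.

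**Step 2. Why Holm keeps the same 5%.** Order the p-values and compare them in turn with 0.05/12, 0.05/11, 0.05/10 and so on up to 0.05, stopping at the first failure. Suppose m0 null hypotheses are true. The first true null to be rejected is met at step m − m0 + 1 at the latest, where the threshold is at most 0.05/m0. The chance that any true-null p-value falls that low is at most m0 × 0.05/m0 = 0.05, whatever the dependence.

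**Step 3. Why Holm never rejects less.** Any p-value at or below 0.05/12 is also below every later Holm threshold, as are all smaller p-values, so Holm reaches it and rejects it.

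**Step 4. Simulation.** Equicorrelated normal change scores, two-sided signed-rank tests by normal approximation, 1,500 to 5,000 runs per setting. With no effect anywhere and m = 12, the family error was 3.8% at correlation 0.5 and 1.8% at 0.8, the same for both methods. Holm kept every Bonferroni rejection in every run.

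Average power per time point at correlation 0.5:

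| Setting | d | Bonferroni | Holm | Gain (points) |
|---|---|---|---|---|
| n = 89, m = 12, effect at all 12 | 0.2 | 13.8% | 17.3% | 3.5 |
| same | 0.3 | 42.8% | 54.0% | 11.2 |
| same | 0.4 | 75.0% | 86.7% | 11.7 |
| same | 0.5 | 94.7% | 98.9% | 4.2 |
| same | 0.6 | 99.3% | 99.9% | 0.6 |
| same | 0.8 | 100% | 100% | 0 |
| n = 89, m = 12, effect at 6 of 12 | 0.3 | 41.9% | 45.1% | 3.2 |
| same | 0.4 | 76.3% | 80.0% | 3.7 |
| n = 89, m = 12, effect at 1 of 12 | 0.4 | 76.2% | 76.2% | 0 |
| n = 89, m = 26, effect at all 26 | 0.3 | 33.8% | 42.7% | 8.9 |
| same | 0.4 | 67.3% | 81.4% | 14.1 |
| same | 0.6 | 98.8% | 100% | 1.2 |
| n = 60, m = 12, effect at all 12 | 0.3 | 23.4% | 29.5% | 6.1 |
| same | 0.4 | 51.9% | 64.5% | 12.6 |
| same | 0.6 | 93.1% | 98.4% | 5.3 |

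At 0.3 to 0.4 SD in the first setting, the gain is 12 × 0.112 = 1.3 to 12 × 0.117 = 1.4 additional time points out of 12. A repeat of the simulation gave 42% to 53% at 0.3 SD and 76% to 87% at 0.4 SD.

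**The case against.** The case for leaving the plan alone is substantial, and most of it stands.

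- Bonferroni controls the stated 5%, and nothing in either document contradicts it. These are post-hoc tests on secondary outcomes in an analysis focused on safety, and the protocol's Data Analysis section says power is not a relevant parameter for an observational study.
- The tests do not carry the conclusion. The effectiveness statement comes from the GLS contrasts, the shape over time from the spline, and means and medians of the decrease are also reported. A patchy set of Bonferroni results would not by itself determine how the time course is read.
- An equal effect at every time point is a favourable case for Holm. It sits awkwardly with a dose that is titrated upward over the first weeks and with the SAP's own reference to a non-linear trend. The simulated changes are normal, while the SAP says the outcomes are not.
- The count of 12 is inferred. The protocol's schedule has 11 in-person post-baseline visits through Month 12 (Study Visits 2 to 12), and they are not evenly monthly.
- The analyses are reported as done. Holm can only add rejections, so swapping it in now without a label would be a data-aware change in one direction.

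A reader might infer that real reductions were missed, and missed for no reason. The documents do not support that: they contain no results, p-values or effect sizes, so a missed reduction is only a possibility under moderate effects. Nor do they show a larger loss for severity, for which no effect size is given. A smaller sample does not uniformly increase the loss either: at 0.3 SD the gain from Holm is 6.1 points with n = 60 and 11.2 with n = 89; at 0.6 SD it is 5.3 and 0.6.

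What remains is the comparison of procedures: Holm has the same error guarantee, at least as many rejections, and gives up no interval the SAP plans.

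**Conclusion.** The point holds as an optional efficiency improvement to a secondary post-hoc analysis. It is not an error in the plan, and no stated claim becomes wrong because of it.

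That Holm dominates Bonferroni is certain; the size of the benefit is conditional. It is about 11 percentage points per time point for sustained effects of 0.3 to 0.4 SD (n = 89, 12 time points, correlation 0.5), and it shrinks to little or nothing when effects are large or confined to few time points. Effect size, correlation, number of comparisons and complete-case sample are all assumptions.

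**What to change.** In the SAP's secondary analysis, replace the Bonferroni correction with Holm-adjusted p-values across the post-baseline time points, separately for seizure frequency and seizure severity, at 5% within each outcome. State the number of time points in each family and how the LOCF repeats are treated. The 5% then applies per outcome and not across both, and the text should say so.

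Where the Bonferroni analysis has already been run, keep it as reported. Put the Holm-adjusted p-values beside it, labelled as a sensitivity analysis chosen after the data were seen.

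The cost is a sentence or two of text and one software option on p-values already computed. The small downside is the disclosure that the Holm results are post-data. Stating the family is worth doing even if Bonferroni is kept, because the correction cannot be checked without the count.

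### The model-based percentage reductions are measured against a spline-fitted month 0 with no baseline term of its own, so they may be biased

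*SAP*

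**What the plan says.** The SAP's single section gives two routes to change from baseline in seizure frequency and severity.

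- **Without a spline.** The listed secondary measures are summaries of the form "Mean (SD) and median (IQR) decrease in seizure frequency as measured in total number of seizures per month", with the same for severity. A Friedman test follows, then Bonferroni-corrected Wilcoxon signed rank tests for "pairwise comparisons between baseline and each post-baseline time point".
- **With a spline.** GLS is fitted to log-transformed measures, and for time "A cubic spline with 4 knots (carefully chosen with AIC and BIC) was put on time to capture the non-linear trend". The other regressors are gender and "several identified baseline clinical variables including number of AEDs, number of AEDs tried, and history of epileptic surgery". On the rows used: "The longitudinal analysis included each month following baseline up to the 12-month endpoint". On the covariance: "AIC and BIC also aided in the choice of the specified correlation structure for this analysis".

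The SAP rests its effectiveness statement on the second route, through "contrast estimates of percentage reduction in seizure outcome measures at each post-baseline time point relative to baseline from model".

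It does not give the knot positions, say whether the spline is restricted, name the correlation structure, or say whether the baseline record is an outcome row. Neither a baseline indicator nor baseline seizure frequency is among the terms named.

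**The concern.** Baseline is off drug and month 1 is on drug. A spline through both must pass smoothly from one to the other, and its value at month 0 is pulled towards the on-drug months. If baseline is not among the fitted rows, nothing in the data fixes month 0. It is then the curve run backwards from month 1.

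The documents make a break at month 0 plausible for a second reason. Under the protocol's Enrollment Visit Procedures, baseline frequency is an average from a historical calendar of at least three months. Follow-up frequency comes from a study diary. The protocol's Data Analysis section itself warns that the historical interval may be overstated. A break caused by the change of source would remain even if the drug effect builds up slowly during titration.

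At stake are the percentage reductions behind the SAP's effectiveness statement. A reader cannot tell from the text whether their error is negligible or tens of points, nor in which direction it runs.

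**Working it through.** The SAP states no percentage reduction, so there is no figure of its own to reproduce. The check asks what the described model would return, on average, when the truth is known.

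**Inputs from the SAP.** Months 0 to 12, log outcome, cubic spline with 4 knots, GLS, contrasts against fitted month 0.

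**Assumed inputs.**
- True reduction at month 12: 50%.
- Onset, either a *step* (50% from month 1) or a *ramp*, mainly linear on the log scale over 2.25 months, roughly the length of the scheduled titration. The ramp's true value at month 1 is 1 − 0.5^(1/2.25) = 26.5%, and it is 50% from month 3.
- Correlation: independence, compound symmetry 0.6, or AR(1) 0.6 to 0.85.

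**Formula.** With μ the true mean log curve, X the spline basis and V the correlation matrix, the expected fit is b = (X′V⁻¹X)⁻¹X′V⁻¹μ. The reading at month m is 100 × [1 − exp(f(m) − f(0))], where f is the fitted curve.

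**Case A: baseline is not an outcome row.**
- Step: log level is ln 0.5 = −0.693 at every month from 1 to 12. A spline fits a constant exactly, so f(0) = −0.693 too. The reading is 1 − exp(−0.693 + 0.693) = 0% at every month.
- Ramp over 2.25 months, true value 50% at month 12: 34% to 41% with a restricted spline at default quantile knots, and about 72% with an unrestricted cubic and four evenly spaced interior knots.
- Ramps over about 2 to 3 months, with other knots and spline forms: from below 0% to about 86% at month 12.

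**Case B: baseline is an outcome row.** True values are 50% at all three months for the step, and 26.5%, 50% and 50% for the ramp.

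| Truth | Spline | Month 1 | Month 3 | Month 12 |
|---|---|---|---|---|
| Step | Restricted, knots at 5/35/65/95% quantiles | 15–21% | 35–47% | 37–48% |
| Step | Restricted, knots 0, 1, 3, 12 | 40–45% | 51–54% | 49–51% |
| Step | Restricted, knots 0, 1, 2, 12 | 46–49% | 51–52% | 50–51% |
| Step | Unrestricted, 4 even interior knots | about 49% | about 49% | about 50% |
| Ramp | Restricted, quantile knots | 18–20% | 42–46% | 47–50% |

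**Knots placed by AIC/BIC.** In 60 simulated trials (N = 89, log-scale SD 1 assumed, baseline in the data), the search under a step chose knots 0, 1, 2, 12 in 59 runs. Mean readings at months 1, 3 and 12 were 48.7%, 51.7% and 51.6%. Under the ramp they were 28.5%, 50.2% and 50.5%.

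**With the fix.** A baseline level plus a spline over months 1 to 12 gives f(0) = 0 and f(m) = −0.693 under the step. The reading is 1 − exp(−0.693) = 50.0% at months 1, 2, 3, 6 and 12.

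**The case against.** The strongest reply is that the text permits readings under which the error is small. The SAP does not call the spline restricted, and it says AIC and BIC guided the knots. With baseline in the data, either an unrestricted cubic with four interior knots or a search over knot positions brings even a sharp step to within a few points. If the criteria chose only the number of knots, at default positions, a sharp step would seldom have led AIC to four: 0% to 15% of simulated runs, against 1% to 32% for BIC. A choice of four is thus weak evidence against a sharp step. Dosing is also titrated, and a ramp is nearly right by month 12. Finally, a contrast relative to baseline can naturally be read as treating baseline as a modelled time point.

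All of this stands as a limit on the size of the problem. It does not remove it. Each reassurance needs baseline to be an outcome row, and the only sentence about the rows points the other way if read literally. If baseline is absent, AIC and BIC cannot detect misfit there. The SAP also does not say that knot positions, rather than their number, were searched.

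A reader might go further and infer that the whole secondary seizure result hangs on knot placement. The documents do not support that. The mean and median decreases and the Friedman and Wilcoxon tests use observed baseline and no spline.

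**Conclusion.** The concern holds as a conditional one. The model-based percentage reductions are contrasts against a fitted month 0 that the listed terms do not tie to observed baseline, so they may be biased. Whether they are depends on choices the SAP does not state.

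- **Baseline not a row:** the error can be large and in either direction.
- **Baseline a row, restricted knots evenly spread, immediate drop:** understatement of about 29 to 35 points at month 1 (50 − 21 and 50 − 15) and 2 to 13 points at month 12 (50 − 48 and 50 − 37).
- **Baseline a row, with early knots or an unrestricted cubic with four interior knots:** about 0 to 4 points at months 3 and 12, and up to 10 points at month 1.
- **Titration-shaped ramp with baseline a row:** about right by month 12.

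Two stronger conclusions are tempting. One is that the reported reductions *are* biased. The documents contain no reported reductions, knots or spline form, so no actual bias can be measured. The other is that any error is conservative. That fails once month 0 is extrapolated, as the 72% and 86% readings show.

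The true curves, the 50% effect, the SD and the correlations are assumptions. The matter affects a secondary outcome in a safety-focused study, but it touches the only analysis on which the SAP rests its effectiveness statement.

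**What to change.** Include the baseline record as an outcome row and give it its own level: a baseline (off-drug) indicator plus the existing spline over months 1 to 12, in the same GLS with the correlation structure chosen as now. Take every percentage-reduction contrast against that level. The comparator then no longer depends on where the knots lie. Smoothing among the on-drug months remains, so month fitted as a 13-level factor is a useful optional sensitivity analysis.

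State in the SAP that baseline is a row, and give the knot positions and the spline form. Showing fitted month 0 beside observed baseline would let readers judge any results already produced from the current model.

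The cost is one extra parameter and slightly wider intervals at single months. Even the 13-level version needs only 12 time parameters, against up to 89 × 13 = 1,157 observations.
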